8.5	MEDICAL MONITORING	24
8.5.1	Internal Data and Safety Monitoring Plan	24
9	DATA HANDLING AND RECORD KEEPING.....	24
9.1	CONFIDENTIALITY	24
9.2	SOURCE DOCUMENTS	24
9.3	CASE REPORT FORMS	25
9.4	RECORDS RETENTION	25
10	STUDY MONITORING, AUDITING, AND INSPECTING	26
10.1	STUDY MONITORING PLAN	26
10.2	AUDITING AND INSPECTING	26
11	ETHICAL CONSIDERATIONS	26
12	STUDY FINANCES	27
12.1	FUNDING SOURCE	27
12.2	SUBJECT STIPENDS OR PAYMENTS	27
13	PUBLICATION PLAN	27
14	REFERENCES	27

List of Abbreviations**LIST OF ABBREVIATIONS**

AE	Adverse Event/Adverse Experience
ANCOVA	Analysis of Covariance
CFR	Code of Federal Regulations
CRF	Case Report Form
DSMB	Data and Safety Monitoring Board
FDA	Food and Drug Administration
GCP	Good Clinical Practice
HIPAA	Health Insurance Portability and Accountability Act
IB	Investigator's Brochure
IND	Investigational New Drug Application
IRB	Institutional Review Board
IUD	Intrauterine Device
IUS	Intrauterine System
PHI	Protected Health Information
PI	Principal Investigator
SAE	Serious Adverse Event/Serious Adverse Experience
SOP	Standard Operating Procedure
LNG-IUS	Levonorgestrel-releasing intrauterine system
TXA	Tranexamic Acid
RCT	Randomized Controlled Trial
HMB	Heavy Menstrual Bleeding
UFS-QOL	Uterine Fibroid Symptom – Quality of Life
MMAS	Menorrhagia Multi-Attribute Scale
PBLAC	Pictorial Blood Loss Assessment Chart
VAS	Visual Analog Scale (for pain)
CI	Confidence Interval
LVCF	Last Value Carry Forward

Study Summary

Title	Prospective Randomized Trial of Tranexamic Acid versus Levonorgestrel Intrauterine System for the Treatment of Heavy Menstrual Bleeding in women with Uterine Fibroids
Running Title	LNG-IUS vs. Tranexamic Acid in women with uterine fibroids
Protocol Number	16-008671
Phase	IV
Methodology	Randomized controlled trial, open label
Overall Study Duration	2 years
Subject Participation Duration	9 months
Single or Multi-Site	Single-site
Objectives	Specific Aim #1 : To determine the comparative effectiveness [as measured by the Menorrhagia Multi-Attribute Scale (MMAS)] and duration of use of TXA versus LNG-IUS for the treatment of HMB in women with uterine fibroids. Specific Aim #2 : To determine the clinical and fibroid-related predictors of successful medical therapy of HMB in women with uterine fibroids.
Number of Subjects	160
Diagnosis and Main Inclusion Criteria	Heavy menstrual bleeding in women with uterine fibroids.
Study Product, Dose, Route, Regimen	Levonorgestrel intrauterine system (20 microgram/24 hour levonorgestrel) Tranexamic acid 1.3 grams three times per day during first 5 days of menses
Duration of Administration	Up to 5 years for the LNG-IUS and up to 1 year for tranexamic acid
Reference therapy	Compared to each other, no placebo arm

Statistical Methodology	
At 3, 6, and 9 months separately, each of the continuously scaled outcomes will be compared between treatment arms based on fitting separate linear regression models and analysis of covariance (ANOCOVA) models will be fit to compare the measures between the two treatment arms after adjusting for baseline levels. Last value carry forward (LVCF) methods will be investigated to accommodate drop-outs. All analyses will be performed based on the intention to treat principle. The cumulative incidence (CI) function will be used to estimate the cumulative proportion of patients by time t who have intentionally discontinued treatment due to the desire or need to stop or switch treatment, after accounting for the competing risk of LNG-IUS expulsion and censoring all other participants at their date of last follow-up or end of study.

----------------------------	--

1 Introduction

This document is a protocol for a human research study. This study will be carried out in accordance with the applicable United States government regulations and Mayo Clinic research policies and procedures.

1.1 Background

Background

Uterine fibroids and especially the heavy menstrual bleeding (HMB) they produce are a common and debilitating problem for women. Our work demonstrates 60% of women with fibroids report that symptoms affect their quality of life and impede physical activity, and 24% report that fibroid symptoms prevent them from reaching their true potential at work (1, 2). HMB, the most common symptom of uterine fibroids, affects approximately 1.4 million women per year and costs an excess \$2,291 per woman annually in lost work and home management activities (3, 4). Medical therapy is the first line treatment for HMB, yet, the lack of evidence of medical efficacy in women with fibroid-related HMB leads to a high rate of surgical management and especially hysterectomy. Fibroids account for more than 40% of hysterectomies in the U.S. which have a 10-12% complication rate and may lead to the detrimental effects of early menopause, even with conservation of the ovaries (5, 6). Randomized studies of the efficacy of medical therapies for HMB typically include only women with few or small fibroids (7, 8). **The goal of this study is to determine the effectiveness of non-estrogenic medical therapy in women with a range of fibroid sizes, locations, and number.**

Two effective medical treatments for HMB have limited data in women with fibroids. The levonorgestrel intrauterine system (LNG-IUS) was FDA approved for the treatment of HMB in 2009 and is highly effective for decreasing menstrual bleeding, treating anemia and improving quality of life (8-10). Moreover, it can be used continuously for 5 years. Expulsion rate in women with fibroids may be as high as 12% and discontinuation rate up to 28% at 2 years based on a small sample size and no information is available about predictors of these events (8).

Tranexamic acid (TXA) is widely used outside the U.S. and was also FDA approved for HMB in 2009; TXA reduces menstrual blood loss in 40% of women and improves quality of life (11-14). In women with fibroids, TXA has been shown to decrease HMB and cause necrosis of the fibroids, especially larger fibroids, which should augment its efficacy for women with fibroids (15).

Our preliminary data from a large insurance-claims database show that women with fibroids were more likely to continue use of LNG-IUS (62% at 6 months) than TXA (22% at 6 months) for the treatment of HMB; however, we were unable to ascertain reasons for discontinuation in either group (16). Accurately predicting which women with fibroids are optimal candidates for medical therapy is a key unanswered question of the Agency for Healthcare Research and Quality (AHRQ) evidence-based review and would have substantial impact on the clinical care for women with fibroids (17).

Thus, we propose a **randomized controlled trial (RCT)** to assess the **comparative effectiveness** of LNG-IUS to TXA for the **treatment of HMB in women with clinically-significant fibroids**. We will measure patient-reported outcomes recognized to be important to women with HMB and study the clinical factors (e.g. body mass index, age) and fibroid factors (e.g. size, location) that predict successful medical therapy.

After greater than 1 year of enrollment and randomization, we have found that we have a higher rate of drop outs in the TXA arm than expected. Nearly all participants in the TXA arm have dropped out (n=4) before 6 months participation due to various side effects. Clinically, we use this medication and do not receive the same reported side effects. Thus, we would like to evaluate the use of TXA in a population that has self-selected the use of the medication. **We will add an observational arm to the study for women who otherwise meet study criteria and select either TXA or LNG-IUS, but decline randomization.**

1.2 Investigational Agent

LNG-IUS was FDA approved for the treatment of HMB in 2009 and previously for contraception in 2000. The LNG-IUS is a T-shaped device with a polyethylene body containing a hormone reservoir, holding a total of 52 mg of levonorgestrel. LNG-IUS initially releases 20 micrograms of the progestin per day, which decreases to less than half that amount after 5 years of use. The levonorgestrel causes stromal pseudodecidualization, decreases endometrial thickness, and lowers uterine vascular density.

TXA was FDA approved for the treatment of HMB in 2009. TXA is a plasminogen-activator inhibitor that blocks fibrinolysis and reduces plasmin activity. A special formulation was designed for the treatment of HMB that reduces gastrointestinal side effects (Brand name *Lysteda*): 1300 mg taken three times per day for up to 5 days of the menstrual cycle (Lukes).

1.3 Clinical Data to Date

Several studies have shown good efficacy of both the LNG-IUS and TXA in the treatment of HMB in the presence of small uterine fibroids {Grigorieva, 2003 #1010} {Gupta, 2015 #992} {Lukes, 2010 #986}. We demonstrated in our large insurance-claims database that women with clinically significant fibroids were more likely to continue use of LNG-IUS (62% at 6 months) than TXA (22% at 6 months) for the treatment of HMB. No studies have demonstrated the reasons for discontinuation of treatment. A case report published after the start of this study shows intratumoral atherosclerosis-like vasculopathy in a fibroid treated with tranexamic acid; no side effects were noted in this case but surgery was done due to lack of response to TXA. The side effects and reasons for discontinuation noted thus far in our study include diarrhea, abdominal cramping, lack of effect, pelvic pain and dysmenorrhea.

1.4 Dose Rationale and Risk/Benefits

Both medications are being used at the clinically acceptable dosages as indicated for the treatment of HMB. Risks of LNG-IUS related to fibroids include expulsion, perforation, or embedment of device. The risk of TXA related to fibroids is necrosis of the fibroids leading to pain.

2 Study Objectives

Primary Objective

To determine the comparative effectiveness [as measured by the Menorrhagia Multi-Attribute Scale (MMAS)] and duration of use of TXA versus LNG-IUS for the treatment of HMB in women with uterine fibroids.

Hypothesis: A user-independent medical therapy (LNG-IUS) will result in better patient reported outcomes and longer use compared to self-administered medication (TXA)

Secondary Objective

To determine the clinical and fibroid-related predictors of successful medical therapy of HMB in women with uterine fibroids.

Hypotheses: Large fibroid size will limit the effectiveness of LNG-IUS compared with TXA; elevated BMI predicts higher success with LNG-IUS over TXA.

[figure not shown]
3 Study Design

3.1 General Design

This is a randomized controlled trial of LNG-IUS compared with TXA for the treatment of HMB in 160 women with uterine fibroids. Subjects with self-reported HMB for 3 months or more that have at least one uterine fibroid >1cm in size that is either intramural or submucosal on ultrasound will be eligible for the study. Clinical evaluation for HMB needs to be completed before enrollment and participants must be eligible for either LNG-IUS or TXA.

Screening for the study will be based on baseline MMAS score with at least one domain scoring >2. Additionally, if not already performed for HMB evaluation, screening will include uterine sounding length, ultrasound documentation of number and size of fibroids, and evaluation of the uterine cavity if indicated. Once consent has been obtained, baseline laboratory studies will be completed and participants randomized to one of two arms. Placement of the LNG-IUS will be performed by study physicians in the clinic setting. Follow-up of treatment effect will continue for 9 months with monthly Pictorial Blood Loss Assessment Card (PBLAC) scores and phone calls at 3 and 6 months. A final visit for evaluation, collection of lab samples, and ultrasound examination will be conducted at 9 months.

For patients that would qualify for the study but choose not to be randomized, we will enroll them into an observation arm. We will have them complete the same questionnaires and report adverse events/side effects at baseline, 3 months, 6 months and 9 months. We will also have them obtain CBC, ferritin, and ultrasound at the end of study. Medications will be provided in the clinical setting and not provided by the study. For patients in the observation arm, the baseline serum creatinine and ultrasound will be done if clinically indicated, but are not required for enrollment.

3.2 Primary Study Endpoints

The primary endpoints are the difference in self-reported MMAS scores at 6 months between LNG-IUS and TXA treatment and the duration of use of TXA versus LNG-IUS

3.3 Secondary Study Endpoints

The secondary endpoints are:

- Patient and fibroid characteristics that predict successful outcomes
- Differences in VAS, PBLAC, UFS-QOL and Rand SF-36 scores

3.4 Primary Safety Endpoints

Safety endpoints include:

1. The correct placement of LNG-IUS based on type of fibroids present, verified by ultrasound after placement of device.
2. Record of side effects or adverse events of each medication based on questionnaire, phone follow-up and self-report.

4 Subject Selection Enrollment and Withdrawal

4.1 Inclusion Criteria

- Premenopausal women aged 25-50
- Seeking treatment for HMB with a completed clinical evaluation
- Image-confirmed uterine fibroids of at least 1 cm in size and either submucosal or intramural
- Monthly menses
- Completed evaluation of HMB within one year
- Able to give consent for inclusion in the study
- Understands the English language for consent and questionnaires
- Self-reported HMB 3 months or more
- Not pregnant or breast-feeding

4.2 Exclusion Criteria

- Class 0 fibroids confirmed by hysteroscopy, saline infused sonogram, or 3D ultrasound
- Uterine sounding length >14 cm
- Abnormal biopsy (pre-malignant or malignant) or incomplete clinical testing to rule out malignancy
- Venous thromboembolic history, clotting disorder, strong family history of venous thromboembolic events
- Needs hormonal contraception, including estrogen-containing medications
- Uterine size >20 weeks gestational size
- Breast, uterine or cervical malignancy
- Liver disease or liver tumor
- Pelvic inflammatory disease or infection with gonorrhea or chlamydia in last 3 months
- Hemoglobin less than 8mg/dL; for women 8-12 mg/dL recommend iron
- Serum creatinine ≥ 1.4

- Pregnant or breast-feeding

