For this study, the study treatment follow-up period is defined as 9 months after enrollment. Events occurring after this visit will be managed clinically. For women with a contraindication to LNG-IUS (e.g. a type I fibroid), we will recommend removal of the LNG-IUS at the 9-month visit to reduce risks.

Preexisting Condition

A preexisting condition is one that is present at the start of the study. A preexisting condition should be recorded as an adverse event if the frequency, intensity, or the character of the condition worsens during the study period.

General Physical Examination Findings

At screening, any clinically significant abnormality should be recorded as a preexisting condition. At the end of the study, any new clinically significant findings/abnormalities that meet the definition of an adverse event must also be recorded and documented as an adverse event.

Post-study Adverse Event

All unresolved adverse events should be followed by the sponsor-investigator until the events are resolved, the subject is lost to follow-up, or the adverse event is otherwise explained. At the last scheduled visit, the sponsor-investigator should instruct each subject to report, to the sponsor-investigator, any subsequent event(s) that the subject, or the subject's personal physician, believes might reasonably be related to participation in this study.

Abnormal Laboratory Values

A clinical laboratory abnormality should be documented as an adverse event if hemoglobin were to drop below 8.0 g/dL during treatment for HMB.

Hospitalization, Prolonged Hospitalization or Surgery

Any adverse event that results in hospitalization or prolonged hospitalization should be documented and reported as a serious adverse event unless specifically instructed otherwise in this protocol. Any condition responsible for surgery should be documented as an adverse event if the condition meets the criteria for an adverse event.

Neither the condition, hospitalization, prolonged hospitalization, nor surgery are reported as an adverse event in the following circumstances:

- Hospitalization or prolonged hospitalization for diagnostic or elective surgical procedures for a preexisting condition. Surgery should **not** be reported as an outcome of an adverse event if the purpose of the surgery was elective or diagnostic and the outcome was uneventful.

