9.3 Case Report Forms

We will use a study case report form (CRF) as the primary data collection instrument for the study. All data requested on the CRF will be recorded and all missing data explained. All entries will be printed legibly in black ink. If any entry error has been made, to correct such an error, we will draw a single straight line through the incorrect entry and enter the correct data above it. All such changes will be initialed and dated. We will not erase or use “white-out” for errors. For clarification of illegible or uncertain entries, we will print the clarification above the item, then initial and date it. If the reason for the correction is not clear or needs additional explanation, we will include the details to justify the correction.

Data Management

We will use the electronic database REDCap to collect and store study-related data including study case report forms. REDCap is password protected and can be used to export the data to a statistical analysis program such as SAS.

Data Processing

Data will be maintained by the small study staff from the data entry into the REDCap system through the analysis in SAS by our statisticians.

Data Security and Confidentiality

All patient information will be de-identified and kept in secure locations where only authorized study personnel can have access. All computers are password protected and secured behind institution firewall. Case report forms will be maintained, in a secure location within the institution campus.

Data Quality Assurance and Clarification Process

Data will be entered by trained personnel with randomly-selected double entry to evaluate data for errors. Validated fields of entry will ensure data ranges are appropriate. Any data queries will be adjudicated by study personnel after review of the original data form.

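### The hemoglobin exclusion limit and iron band in section 4.2 are printed in mg/dL and should be in g/dL, a factor of 1000

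*Combined protocol and SAP*

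**What the plan says.** The exclusion list in section 4.2 contains one hemoglobin entry: "Hemoglobin less than 8mg/dL; for women 8-12 mg/dL recommend iron". It does two jobs. It sets a lower limit for entry, and it sets a band in which a woman may enter but should be advised to take iron. Both are given in mg/dL.

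Section 8.1, under Abnormal Laboratory Values, tells the study team to record a laboratory adverse event "if hemoglobin were to drop below 8.0 g/dL during treatment for HMB". The number is again 8; the unit is g/dL.

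The statistical methods in section 7.2 name hemoglobin as a continuous outcome without giving a unit. Table 1 in section 6 lists only a CBC. No other section restates the entry limit or the iron band.

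**The concern.** Two safety limits for one analyte carry the same number and units that differ by a factor of 1000. They cannot both be right, and the one in the exclusion list makes no clinical sense.

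The trial enrolls women with heavy menstrual bleeding, so anemia is a central safety matter. Section 8 counts worsening anemia or transfusion as a safety endpoint, and section 4.4.1 provides for other treatment if clinically significant anemia develops. The section 4.2 bullet is the only numerical hemoglobin limit at entry and the only iron instruction in the document.

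What is at stake is the written criterion. Monitoring, audit and inspection under section 10 refer to the protocol text. On that text, enrolling a severely anemic woman would not be a deviation, although the criterion plainly exists to keep her out. The hemoglobin used at entry may also come from a clinical CBC up to 3 months old (Table 1, footnote 2), so the criterion is applied to results taken from the clinical record, and its unit should match them.

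**Working it through.** **Inputs**

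- Entry limit, section 4.2: below 8 mg/dL.
- Iron band, section 4.2: "for women 8-12 mg/dL recommend iron".
- Adverse-event limit, section 8.1: below 8.0 g/dL.
- Conversion: 1 g = 1000 mg, so a value in g/dL equals the value in mg/dL divided by 1000.

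**Section 4.2 as printed, converted to g/dL**

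- Entry limit: 8 / 1000 = 0.008 g/dL.
- Upper end of the iron band: 12 / 1000 = 0.012 g/dL.
- Ratio of the section 8.1 limit to the printed entry limit: 8.0 / 0.008 = 1000.

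**Section 4.2 as evidently intended, converted to mg/dL**

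- Entry limit: 8 × 1000 = 8,000 mg/dL.
- Iron band: 8 × 1000 to 12 × 1000 = 8,000 to 12,000 mg/dL.

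| Limit | As printed | In g/dL as printed | As intended |
|---|---|---|---|
| Exclude below | 8 mg/dL | 0.008 g/dL | 8 g/dL |
| Recommend iron | 8–12 mg/dL | 0.008–0.012 g/dL | 8–12 g/dL |
| Adverse event below (8.1) | 8.0 g/dL | 8.0 g/dL | 8.0 g/dL |

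**Effect of a literal reading**

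- A woman at 7 g/dL has 7 × 1000 = 7,000 mg/dL. That is not below 8 mg/dL, so she is not excluded, yet she enters already under the adverse-event limit in section 8.1.
- A woman at 10 g/dL has 10,000 mg/dL. That lies outside 8–12 mg/dL, so the iron advice does not reach her.

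**Which unit is meant**

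With g/dL, the entry limit in section 4.2 equals the on-treatment limit in section 8.1, and a band just above the exclusion limit in which iron is advised is a sensible instruction. With mg/dL, neither holds. The upper value of 12 appears nowhere else in the document, but the band starts at the exclusion limit, so it must share that limit's unit.

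**Is it an artifact?**

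The unit occurs twice in the bullet, with different spacing before it, so a text-extraction fault is unlikely. The bullet is current text, not part of a change log, and nothing in it is redacted.

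**The case against.** The strongest reply is that this is a clerical slip with no demonstrated consequence. The trial is single-site and recruits through gynecology clinics. Nobody there would look for a hemoglobin of 0.008 g/dL, and the one unit the protocol states elsewhere for hemoglobin is g/dL, so the document largely resolves the ambiguity itself. A form that simply compares the CBC value with 8 would exclude the right women. That stands, and it is why the point is minor.

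It is also fair that section 8.1 is an on-treatment reporting rule and does not restate the entry criterion, so the link between the two limits is an inference. It is a strong one, since the analyte and the number are the same and no other reading is workable.

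Two supporting links deserve little weight. The 3-month CBC window concerns the age of a result, not its unit. Section 9.3 says only that "Validated fields of entry will ensure data ranges are appropriate"; it names neither hemoglobin nor a unit, and the forms are not in the document. A field range-checked in mg/dL would probably reject every real value and so expose the slip. These are reasons to look at the form, not evidence that it is wrong.

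Finally, the iron half of the bullet is advice, not an eligibility condition, and the anemia provisions in sections 4.4.1 and 8 do not depend on this unit. All true. None of it makes the printed exclusion limit correct.

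**Conclusion.** The concern holds. Section 4.2 gives the wrong unit for both the hemoglobin exclusion limit and the iron band, each by a factor of 1000, and followed to the letter the bullet does nothing. Severity is minor.

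The conclusion that g/dL is intended rests on the shared value of 8 in section 8.1 and on the iron advice being workable only in that unit. The expectation of no effect on enrollment assumes that staff apply g/dL, which is likely but is not shown by the document. No sample-size, power, endpoint or analysis statement depends on the limit.

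**What to change.** In the section 4.2 bullet, change mg/dL to g/dL in both places: exclude hemoglobin below 8 g/dL, and recommend iron at 8–12 g/dL. Then confirm that the eligibility form and the REDCap hemoglobin field are labelled and range-checked in g/dL.

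The cost is a one-line protocol correction and a check of one form field. There is no trade-off, and no statistical section needs to change.
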